2.4.7 Analyses of Immunogenicity

The baseline value used to define ADA variables is the original baseline from the parent study. The ADA analyses will be performed for each analysis set ([Section 2](#)) of ADA population ([Section 2.3.4](#)) by treatment category.

The ADA variables described in [Section 2.1.6](#) will be summarized using descriptive statistics. Frequency tables of the proportion of patients developing ADA positivity in the ADA assay, neutralizing antibody status in the NAb assay, pre-existing immunoreactivity, treatment-emergent, treatment-boosted, persistent, indeterminate, transient ADA responses and titers will be presented.

Listing of all ADA maximum titer levels and neutralizing antibody status will be provided for ADA positive patients.

ADA variable will be summarized by baseline weight group (≤ 30 , > 30 kg).

If there were patients who had a long gap between the parent EOT visit and the first dose in LTS14424 study, additional analyses excluding such patients may be conducted for the status in the ADA assay in the current study on the full analysis set of ADA population.

2.4.7.1 Status in the ADA assay at baseline of the parent study

The following summary will be provided for each analysis set of ADA population by the treatment category:

- Number (%) of patients negative in the ADA assay at baseline of parent study.
- Number (%) of patients positive in the ADA assay at baseline of parent study:
 - The summary statistics (including number, median, Q1, Q3, minimum and maximum) of the titer for the patients positive in the ADA assay at baseline of the parent study,
 - Number (%) of patients with neutralizing antibody status (negative or positive in the NAb assay).

2.4.7.2 Status in the ADA assay in the current study

The following summary will be provided based on each analysis set of ADA population by the treatment category:

- Number (%) of patients with ADA status (negative or positive in the ADA assay) at time points analyzed:
 - The summary statistics (including number, median, Q1, Q3, minimum and maximum) of the maximum post-baseline titer for ADA positive patients,
 - ADA titers using descriptive statistics (median, Q1, Q3, minimum and maximum) at ADA time points analyzed,
 - Number (%) of patients with neutralizing antibody status (negative or positive in the NAb assay) for the ADA positive patients.
- Number (%) of patients with pre-existing immunoreactivity.
- Number (%) of patients with treatment-boosted anti-drug antibodies:
 - The summary statistics (including number, median, Q1, Q3, minimum and maximum) of the maximum post-baseline titer for treatment-boosted ADA patients.
- Number (%) of patients with treatment-emergent ADA:
 - The summary statistics (including number, median, Q1, Q3, minimum and maximum) of the maximum post-baseline titer for treatment-emergent positive patients,
 - Number (%) of patients in the low, moderate or high titer category with treatment-emergent positive response,

- Number (%) of patients with transient, indeterminate, or persistent treatment-emergent ADA response.
- Number (%) of patients with neutralizing antibody results (negative or positive in the NAb assay).

2.4.7.3 Impact of ADA on clinical safety

The safety assessment will focus on the following events:

- Serious or severe injection site reactions (ISRs) that last longer than 24 hours.
- Hypersensitivity reactions (SMQ hypersensitivity narrow search and confirmed by medical review).
- Anaphylactic reactions (SMQ anaphylactic reaction narrow search).

Correlations between ADA variables (eg, ADA maximum titers, neutralizing antibody status, treatment-emergent, treatment-boosted, transient, indeterminate and persistent ADA responses) and safety may be explored.

2.4.7.4 Impact of ADA on clinical efficacy

Correlations between ADA variables (eg, ADA maximum titers, neutralizing antibody status, treatment-emergent, treatment-boosted, transient, indeterminate and persistent ADA responses) and efficacy endpoints may be explored for each analysis set of ADA population by the treatment category:

- Annualized rate of severe exacerbation events.
- Change from baseline in % predicted FEV1.

2.4.7.5 Impact of ADA on PK

Associations between ADA variables (eg, ADA maximum titers, neutralizing antibody status) and descriptive summaries of concentration of dupilumab in serum may be explored for each analysis set of safety population by the treatment category. Plot of individual concentration-time profiles of functional dupilumab in serum over visits may also be provided by ADA classifications (negative at all time, pre-existing immunoreactivity, treatment-boosted anti-drug antibodies, and treatment-emergent anti-drug antibodies [further separated by NAb status and maximum titer category]) for each analysis set of safety population by the treatment category.

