In a completed Phase 2b dose ranging study (DRI12544), dupilumab efficacy at 4 dose regimens (300 mg once every 4 weeks [q4w] and once every 2 weeks [q2w], and 200 mg q2w and q4w with a total dose on Day 1 of 600 mg [for the 300 mg regimen] and 400 mg [for the 200 mg regimen]) was evaluated in adult patients with uncontrolled asthma while receiving a stable dose of medium to high-dose ICS/LABA in addition to their study treatment (placebo or dupilumab). Dupilumab demonstrated dose dependent improvement, compared with placebo, in the change from baseline in FEV1 at Week 12. In addition, consistent efficacy results in favor of dupilumab over placebo were observed in the majority of main secondary efficacy endpoints including annualized rate of severe exacerbation events. The maximum treatment effects were observed in the 200 mg and 300 mg q2w regimens. Exposure-response analyses further supported the maximal effect for both endpoints of FEV1 and severe exacerbation rate approached/achieved at the steady-state exposure of the two q2w regimens (mean steady-state trough concentrations of 28.3 and 58.5 mg/L, respectively). Dupilumab was observed to be well tolerated and had an acceptable safety profile across all dose regimens examined. Treatment-emergent adverse events (TEAE) were reported in 79.1% patients in the dupilumab groups (75.3% to 82.8%) and 74.7% patients in the placebo group. The most frequently reported TEAEs included injection site reactions (ISR), respiratory tract infections and related symptoms, headache, and back pain. There was no apparent dose relationship for any particular TEAE except for ISR, majority of which were mild in nature (5).

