11.4.4.1 Pharmacokinetic analysis

The PK analyses will be performed in the two analysis sets for PK population as defined in [Section 11.4](#) by the dose regimen. The baseline value of each applicable PK variable is the original baseline from the parent study. Serum concentrations of functional dupilumab will be summarized using arithmetic and geometric means, SD, standard error of the mean (SEM), coefficient of variation, minimum, maximum, and median.

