2 STATISTICAL AND ANALYTICAL PROCEDURES

Generalities

Generally, for each analysis population (Safety, Efficacy, Pharmacokinetics, and Anti-drug antibody) that is defined in [Section 2.3](#), the planned analyses will be conducted in the following two analysis sets:

- The full analysis set: all data observed in the study. The analyses performed on the full analysis set are to evaluate the long-term safety, efficacy, PK and etc. of all the dose regimens that are investigated in the LTS14424 study, that is, dupilumab 100 mg q2w, 300 mg q4w and 200 mg q2w.
- The modified analysis set: 1) For patients never exposed to 300 mg q4w: all observed data will be included 2) For patients that switch from 100 mg q2w to 300mg q4w in LTS14424: data will be included up to the date of first dose of 300 mg q4w with censoring data observed on or after this date 3) For patients that initiate the study on 300 mg q4w (i.e. receive 300 mg q4w at Day 0) no data will be included in this analysis set. The analyses performed on the modified analysis set are to focus on the long-term safety, efficacy, PK and etc. of the same regimens as the parent study, that is, dupilumab 100 mg q2w and 200 mg q2w.

Observation period

The observation period will be divided into 4 epochs which are defined in [Table 3](#) according to the two analysis sets.

The treatment-emergent adverse event period will include both treatment and residual treatment epochs that are defined in [Table 3](#). The post-treatment adverse event period will be the post-treatment epoch.

The pre-treatment adverse event period will be from the start of AE reporting in LTS14424 up to the first dose of IMP in LTS14424. For all the periods aforementioned, both date and time shall be used in the determination of the periods, as long as they will be available.

Table 3 - Study epoch definition by analysis set

| Analysis Set | Epoch | Applicable Patients | Epoch Start | Epoch End |
|-------------------|--------------------|---------------------------------------------------|-----------------------------------|-----------------------------------------------|
| Full analysis set | Screening | All | – | The day before the date of first IMP |
| | Treatment | Patients with last IMP on 100mg/200mg q2w regimen | Date of the first IMP in LTS14424 | Date of last IMP +14 days |
| | | Patients with last IMP on 300 mg q4w regimen | Date of the first IMP in LTS14424 | Date of last IMP +28 days |

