2.4 STATISTICAL METHODS

Generalities

For each analysis set defined in [Section 2](#), the planned analyses will be presented by below treatment categories according to the actual treatment groups in the parent study EFC14153:

- Placebo-Dupilumab, defined as the patients who have been in the actual placebo arm of the parent study and exposed to dupilumab in LTS14424.
- Dupilumab-Dupilumab, defined as the patients who have been in the actual dupilumab arm of the parent study and exposed to dupilumab in LTS14424.
- All, defined as all patients from Placebo-Dupilumab and Dupilumab-Dupilumab categories.

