2.4.6.1 Pharmacokinetic analysis

The PK analyses will be performed for each analysis set ([Section 2](#)) of PK population ([Section 2.3.3](#)).

For the full analysis set, PK analysis will be presented in the PK population by visit according to the dose regimen (100 mg q2w or 200 mg q2w or 300 mg q4w) to which the PK sampling is exposed. That is if a patient is switched from 100 mg q2w to 200 mg q2w, the results from PK sampling before or on date of the switch will be summarized in 100 mg q2w group and results from PK sampling after the switch will be summarized in 200 mg q2w group. Similarly, if a patient is switched from 100 mg q2w to 300 mg q4w, the results from PK sampling before or on date of the switch will be summarized in 100 mg q2w group and results from PK sampling after the switch will be summarized in 300 mg q4w group.

Similarly for modified analysis set, PK analysis will be presented in PK population by visit according to the dose regimen (100 mg q2w, 200 mg q2w) to which the PK sampling is exposed at each visit.

Serum concentrations of dupilumab will be summarized using arithmetic and geometric means, SD, standard error of the mean (SEM), coefficient of variation (CV), minimum, median and

maximum by visit. If date and/or time of the drug intake and/or sampling are missing, then the concentration will not be taken into account. For the patients from the Dupilumab arm of parent study, one-half of LLOQ will be used if the pre-dose concentration values at Week 0 of LTS14424 are below the lower limit of quantitation (LLOQ = 78 ng/ml); For the patients from the Placebo arms of parent study, the pre-dose concentration value at Week 0 of LTS14424 should use 0 if the pre-dose concentration values at Week 0 of LTS14424 are below the lower limit of quantitation. Values will be expressed in the tables with no more than three significant figures.

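### SAP 2.4.7.5 compares dupilumab concentration between ADA classes by parent-study arm and not by dose regimen, so a regimen difference could pass for an ADA effect or mask one

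*SAP*

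**What the plan says.** Main SAP 2.4.7.5 (Impact of ADA on PK) has two optional outputs. The first relates ADA variables to concentration: "descriptive summaries of concentration of dupilumab in serum may be explored for each analysis set of safety population by the treatment category". The second is graphical: "Plot of individual concentration-time profiles of functional dupilumab in serum over visits may also be provided by ADA classifications", again for each analysis set and treatment category. Neither mentions dose regimen.

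SAP 2.4 defines the grouping factor: "the planned analyses will be presented by below treatment categories according to the actual treatment groups in the parent study EFC14153". The categories are Placebo-Dupilumab, Dupilumab-Dupilumab and All.

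SAP 2 defines the analysis sets. The full set covers "all the dose regimens that are investigated in the LTS14424 study, that is, dupilumab 100 mg q2w, 300 mg q4w and 200 mg q2w". By contrast, the modified set covers "the same regimens as the parent study, that is, dupilumab 100 mg q2w and 200 mg q2w".

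The main PK analysis is organized differently. SAP 2.4.6.1 says "PK analysis will be presented in the PK population by visit according to the dose regimen". It adds a rule for children who change regimen: samples up to and including the switch date count under the old regimen, later samples under the new one. Protocol 11.4.4.1 likewise places the PK analyses "by the dose regimen. The baseline value of each applicable PK variable is the original baseline from the parent study". Protocol 11.4.4.2 makes the assessment of ADA impact on PK optional and leaves the ADA detail to the SAP.

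**The concern.** The purpose of 2.4.7.5 is to see whether children who develop ADA have lower drug exposure. Concentration also depends on regimen, which is why the main PK tables are split that way. Parent-study arm does not determine regimen in this study; body weight and the timing of the dose change do (protocol 8.1.1 and 8.4). Each parent-arm category can therefore contain children on different regimens.

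If ADA-positive children are over-represented on the regimen with lower concentrations, the pooled comparison shows a loss of exposure that ADA did not cause. If they are over-represented on the regimen with higher concentrations, a real loss can disappear.

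Switching adds a second problem. A child who moves between regimens carries one ADA classification but contributes concentrations from two regimens. On a profile with no regimen label, a step caused by the switch cannot be told from one caused by ADA.

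**Working it through.** **1. Is the regimen split carried over?** Section 2.4.6.1 groups by regimen at sampling and has a switch rule. Section 2.4.7.5 groups by analysis set, treatment category and ADA class, and does not refer to that rule. The nearest mitigation is in 2.4.7, where ADA variables are summarized by baseline weight group (≤30, >30 kg). That split applies to ADA variables, not to concentrations by ADA class. It also uses parent-study baseline weight, which is not the regimen at sampling. The split is not carried over.

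**2. Which regimens are pooled?** The modified set pools 100 and 200 mg q2w. The full set adds 300 mg q4w, but SAP 1.6 (Table 2) reports that very few patients received it and that the two sets overlap heavily. The contrast is mainly 100 versus 200 mg q2w.

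**3. How large could the distortion be?** The plan has no figure to reproduce here. Take two regimens and no ADA effect within either. Let *r* be the concentration on the higher-exposure regimen divided by that on the lower. Let *a* and *b* be the shares of ADA-positive and ADA-negative samples from the lower-exposure regimen. Then

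apparent ratio (ADA-positive / ADA-negative) = [a + (1 − a)r] / [b + (1 − b)r]

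Inputs:
- *a* = 0.50 and *b* = 0.30 are assumptions.
- *r* is not given for children, so it is varied from 1.0 upward.
- The top value comes from protocol 4.2, which reports adult "mean steady-state trough concentrations of 28.3 and 58.5 mg/L, respectively", for 200 and 300 mg q2w: 58.5 / 28.3 = 2.07.

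| r | Calculation | Apparent ratio | Apparent loss |
|---|---|---|---|
| 1.00 | 1.000 / 1.000 | 1.000 | 0% |
| 1.25 | (0.50 + 0.625) / (0.30 + 0.875) = 1.125 / 1.175 | 0.957 | 4% |
| 1.50 | (0.50 + 0.750) / (0.30 + 1.050) = 1.250 / 1.350 | 0.926 | 7% |
| 2.07 | (0.50 + 1.035) / (0.30 + 1.449) = 1.535 / 1.749 | 0.878 | 12% |

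With *b* held at 0.30, moving *a* from 0.40 to 0.60 gives a loss of 2% to 6% at *r* = 1.25 and 6% to 18% at *r* = 2.07.

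**4. Opposite direction.** Exchanging the shares (*a* = 0.30, *b* = 0.50) inverts the ratios: 1.175 / 1.125 = 1.044 at *r* = 1.25 and 1.749 / 1.535 = 1.139 at *r* = 2.07. A true loss of 4% or 12% respectively would then be cancelled.

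**5. Cross-check through ADA incidence.** Assume half of the children are on the lower-exposure regimen, with ADA incidence 10% there and 5% on the other. At *r* = 1.25:
- ADA-positive mean = (0.5 × 0.10 × 1 + 0.5 × 0.05 × 1.25) / 0.075 = 1.083
- ADA-negative mean = (0.5 × 0.90 × 1 + 0.5 × 0.95 × 1.25) / 0.925 = 1.128
- Ratio = 0.960

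An apparent loss of 4% again. With equal ADA incidence or equal concentration across regimens, the ratio is exactly 1.

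**6. After stratification.** Within each regimen the ratio is 1.00 by construction, because the illustration contains no ADA effect.

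**The case against.** The strongest objection concerns size. The 2.07 ratio compares adult 200 with adult 300 mg q2w, and 300 mg q2w is not used in this study. Here the two q2w doses are tiered by weight. Taking 16 kg as the smallest child (protocol 9.3), 100 mg is 100/30 = 3.3 to 100/16 = 6.3 mg/kg. Taking 60 kg as an assumed upper weight, 200 mg is 200/60 = 3.3 to 200/30 = 6.7 mg/kg. These ranges nearly coincide. That does not prove equal troughs, but it gives no support for a two-fold gap. This part of the objection stands, so 2.07 marks only the upper end of an illustration.

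The confounding is also conditional, since it needs both concentration and ADA class to differ by regimen. A reader could partly check this from the regimen-specific PK tables and the ADA tables by weight group. That is fair, but those tables do not stratify the comparison itself.

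The analysis is optional and descriptive. That limits the importance of the point, not its correctness.

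Two practical objections also stand. Bias in a pooled mean does not carry over directly to individual profiles, and splitting profiles into regimen panels would cut a switching child's curve. Also, regimen strata on top of ADA classes that are further divided by neutralizing status and titer would leave some cells nearly empty. The fix allows for both.

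A reader might infer that naming the safety population in 2.4.7.5 adds bias, because it includes children with no concentration or ADA result. The documents do not support that. SAP 2.5.2 uses observed data only, so such children cannot enter a concentration-by-ADA-class summary. It is a wording inconsistency with the PK and ADA populations used elsewhere.

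**Conclusion.** The point holds as a minor, inexpensive improvement. As written, the grouping in 2.4.7.5 cannot separate an ADA effect on concentration from a regimen effect, and the plan already has the rule that would do so.

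The size is unknown. With assumed shares of 50% versus 30%, the apparent difference is 0%, about 4% and about 12% at concentration ratios of 1.0, 1.25 and 2.07. The shares are assumed, and the last ratio is from adults on a pair of regimens not used together here.

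Two stronger readings are tempting and unsupported. One is that a distortion of about 12% should be expected; nothing in the documents shows that concentration or ADA incidence differs by regimen in these children. The other is that three regimens are mixed throughout; this is true only of the full analysis set, where few children received 300 mg q4w.

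What is affected is the interpretation of one exploratory analysis, if it is run.

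**What to change.** Amend main SAP 2.4.7.5 so that, if the analysis is run:

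- concentrations after the first dose in LTS14424 are summarized by ADA class within the dose regimen at sampling, using the assignment rule of 2.4.6.1;
- ADA subclasses (neutralizing status, titer category) are collapsed where cells are sparse;
- each child's concentration-time profile is kept whole, with the regimen and any switch marked on the curve;
- the population wording is aligned with the PK and ADA populations, for consistency only.

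The change needs no new data. The cost is SAP wording and smaller cells, most of all for 300 mg q4w, where the output may be little more than individual profiles.

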2.5 DATA HANDLING CONVENTIONS

2.5.1 General conventions

The following formulas will be used for computation of parameters.

Demographic formulas

Baseline age is calculated as following:

$$\text{Baseline age} = \text{integer part of (informed consent date of parent study} - \text{birth date})/365.25$$

Age of onset of asthma is calculated as following:

$$\text{Age of onset of asthma} = \text{integer part of (asthma onset date prior to parent study} - \text{birth date})/365.25$$

BMI is calculated as following:

$$\text{BMI} = \text{Weight in kg} / (\text{height}^2 \text{ in meters})$$

Renal function formulas

Creatinine clearance (CLcr) value will be derived using the equation of glomerular filtration rate (GFR) Bedside Schwartz

$$\text{GFR (mL/min/1.73 m}^2\text{)} = \text{k} \times \text{height (cm)} / \text{sCr (standardized serum creatinine, mg/dL)},$$

where the coefficient k=0.55 for patients ≥ 6 and < 12 years old, 0.65 for adolescent (≥ 12 years old) male patients, or k=0.55 for adolescent (≥ 12 years old) female patients.

2.5.2 Missing data

For categorical variables, patients with missing data are not included in calculations of percentages unless otherwise specified. When relevant, the number of patients with missing data is presented.

As per the study design, the statistical method of the data analyses for LTS14424 study is based on the descriptive summary statistics using observed data only; and, no model-based imputation for missing data will be performed. The missing scheduled assessment(s) or visit(s) due to the COVID-19 pandemic will be documented in the protocol deviations.

Handling of computation of treatment duration if investigational medicinal product end of treatment date is missing

For the calculation of the treatment duration, the date of the last dose of IMP is equal to the date of last administration reported on eCRF page “Treatment Status”. If this date is missing, the exposure duration should be left as missing.

The last dose intake should be clearly identified in the eCRF and should not be approximated by the last returned package date.

Handling of medication missing/partial dates

No imputation of medication start/end dates or times will be performed. If a medication date or time is missing or partially missing and it cannot be determined whether it was taken prior or concomitantly, it will be considered a prior and concomitant medication.

Handling of adverse events with missing or partial date/time of onset

Missing or partial adverse event onset dates and times will be imputed so that if the partial adverse event onset date/time information does not indicate that the adverse event started prior to treatment or after the treatment-emergent adverse event period, the adverse event will be classified as treatment-emergent. No imputation of adverse event end dates/times will be performed. These data imputations are for categorization purpose only and will not be used in listings. No imputation is planned for date/time of adverse event resolution.

Handling of adverse events when date and time of first investigational medicinal product administration is missing

When the date and time of the first IMP administration is missing, all adverse events that occurred on or after the day of enrollment of LTS14424 should be considered as treatment-emergent adverse events. The exposure duration should be kept as missing.

The last dose intake should be clearly identified in the case report form and should not be approximated by the last returned package date.

Handling of missing assessment of relationship of adverse events to investigational medicinal product

If the assessment of the relationship to IMP is missing, then the relationship to IMP has to be assumed and the adverse event considered as such in the frequency tables of possibly related adverse events, but no imputation should be done at the data level.

Handling of missing severity/grades of adverse events

If the severity/grade is missing for 1 of the treatment-emergent occurrences of an adverse event, the maximal severity on the remaining occurrences will be considered. If the severity is missing for all the occurrences, a “missing” category will be added in the summary table.

Handling of potentially clinically significant abnormalities

If a patient has a missing baseline he will be grouped in the category “normal/missing at baseline.”

For PCSAs with 2 conditions, one based on a change from baseline value or a normal range and the other on a threshold value, with the first condition being missing, the PCSA will be based only on the second condition.

For a PCSA defined on a threshold and/or a normal range, this PCSA will be derived using this threshold if the normal range is missing; eg, for eosinophils the PCSA is > 0.5 Giga/L or $>\text{ULN}$ if $\text{ULN} \geq 0.5$ Giga/L. When ULN is missing, the value 0.5 should be used.

Measurements flagged as invalid by the laboratory will not be summarized or taken into account in the computation of PCSA values.

